**Table 6-3 Dose modification guidelines**

	Ribociclib/placebo ( 3 weeks on/1 week off schedule)		Fulvestrant	
	Dose	Number of capsules & strength	Dose	Number of injections & strength
Starting dose	600 mg	3 x 200 mg capsules	500 mg	2 x 250mg (5 mL) injections
First dose reduction	400 mg	2 x 200 mg capsules	No dose modification allowed	
Second dose reduction	200 mg	1 x 200 mg capsules	No dose modification allowed	

Clinical judgment of the treating physician should guide the management plan of each patient based on individual benefit/risk assessment. However, for events requiring a discontinuation in [Table 6-4](#), [Table 6-5](#), [Table 6-6](#), [Table 6-7](#) and [Table 6-8](#) or listed in [Section 7.1.3](#), treatment must be discontinued.

Unscheduled local laboratory assessments may be performed if medically indicated to document a (potential) adverse event or when the treating physician cannot wait for central laboratory results for decision making (e.g. dose modifications). In this particular situation, if possible, the blood sample obtained at the same time point should be submitted to the central laboratory for analysis in parallel with local analysis.

The results of the local laboratory will be recorded in the eCRF if any of the following criteria are met:

[figure not shown]
- A treatment decision was made based on the local results, or
- Local lab results document an adverse event not reported by the central lab, or
- Local lab results document an adverse event severity is worse than the one reported by the central lab, or
- There are no concomitant central results available.

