Increase from baseline grade 0 or 1 to grade 2 ( $> 3.0 - 5.0 \times \text{ULN}$ )	Dose interruption of ribociclib/placebo If resolved to $\leq$ baseline grade in $\leq 21$ days, then maintain dose level If resolved to $\leq$ baseline grade in $> 21$ days or toxicity recurs, then reduce 1 dose level Repeat liver enzyme and bilirubin tests twice weekly for 2 weeks after dose resumption If toxicity recurs after two dose reductions or recovery to $\leq$ baseline grade is $> 28$ days, discontinue ribociclib/placebo
Increase from baseline grade 0 or 1 to grade 3 ( $> 5.0 - 20.0 \times \text{ULN}$ )	Dose interruption of ribociclib/placebo until resolved to $\leq$ baseline grade, then lower 1 dose level of ribociclib/placebo  Repeat liver enzyme and bilirubin tests twice weekly for 2 weeks after dose resumption  If recovery to $\leq$ baseline grade is $> 28$ days, discontinue ribociclib/placebo If toxicity recurs, discontinue ribociclib/placebo
Increase from baseline grade 2 to grade 3 ( $> 5.0 - 20.0 \times \text{ULN}$ )	Dose interruption of ribociclib until resolved to $\leq$ baseline grade, then lower 1 dose level of ribociclib/placebo Repeat liver enzyme and bilirubin tests twice weekly for 2 weeks after dose resumption  If toxicity recurs after two dose reductions or recovery to $\leq$ baseline grade is $> 28$ days, discontinue ribociclib./placebo
Grade 4 ( $> 20.0 \times \text{ULN}$ )	Discontinue ribociclib/placebo
AST or ALT and concurrent Bilirubin	

For patients with normal ALT and AST and total bilirubin at baseline: AST or ALT > 3 x ULN combined with total bilirubin > 2 x ULN without evidence of cholestasis or For patient with elevated AST or ALT or total bilirubin at baseline: baseline : [AST or ALT >2 x baseline AND >3.0x ULN] OR [AST or ALT 8.0 x ULN]- whichever is lower- combined with [total bilirubin >2 x baseline AND >2.0 x ULN]
	
Discontinue ribociclib/placebo

Confounding factors and/or alternative causes for increased transaminases should be excluded before dose interruption/reduction. They include but are not limited to: concomitant medications, herbal preparations or dietary supplements, infection, hepato-biliary disorder or obstruction, new or progressive liver metastasis, and alcohol intake.
	

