### 6.5.1.2.1 Additional follow-up for hepatic toxicities

Increase in transaminases combined with total bilirubin (TBIL) increase may be indicative of drug-induced liver injury (DILI), and should be considered as clinically important events. The threshold for potential DILI may depend on the patient's baseline AST/ALT and TBIL value; patients meeting any of the following criteria will require further follow-up as outlined below:

- For patients with normal ALT and AST and TBIL value at baseline: AST or ALT > 3.0 x ULN combined with TBIL > 2.0 x ULN
- For patients with elevated AST or ALT or TBIL value at baseline: [AST or ALT > 2 x baseline AND > 3.0 x ULN] OR [AST or ALT > 8.0 x ULN], whichever is lower, combined with [TBIL > 2 x baseline AND > 2.0 x ULN]

Medical review needs to ensure that liver test elevations are not caused by cholestasis, defined as: ALP elevation > 2.0 x ULN with R value < 2 in patients without bone metastasis, or elevation of ALP liver fraction in patients with bone metastasis.

[figure not shown]
Note: The R value is calculated by dividing the ALT by the ALP, using multiples of the ULN for both values. It denotes the relative pattern of ALT and/or ALP elevation is due to cholestatic or hepatocellular liver injury or mixed type injury.

In the absence of cholestasis, these patients must be immediately discontinued from study drug treatment, and repeat LFT testing as soon as possible, preferably within 48 hours from the awareness of the abnormal results. The evaluation should include laboratory tests, detailed history, physical assessment and the possibility of liver metastasis or new liver lesions, obstructions/compressions, etc.

Hepatic toxicity monitoring includes the following LFTs: albumin, ALT, AST, total bilirubin, direct and indirect bilirubin, alkaline phosphatase (fractionated if alkaline phosphatase is grade 2 or higher), creatine kinase, prothrombin time (PT)/INR and GGT. For patients with Gilbert Syndrome: total and direct bilirubin must be monitored, intensified monitoring applies to changes in direct bilirubin only.

Close observation is recommended in case of AST, ALT, and/or bilirubin increase requiring dose interruption, which involves:

- Repeating liver enzyme and serum bilirubin tests **two or three times weekly**. After dose resumption repeat liver enzyme and bilirubin tests twice weekly during the first 2 weeks,

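### For patients with elevated baseline liver tests, Table 6-5 mandates discontinuation regardless of cholestasis, Section 6.5.1.2.1 mandates it only when cholestasis is absent, and nothing says which governs

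*Protocol*

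**What the plan says.** **Table 6-5, combined AST/ALT and bilirubin row.** Two criteria are joined by *or*, and both carry the single action "discontinue ribociclib/placebo". The text at the join is "without evidence of cholestasis or For patient with elevated AST or ALT or total bilirubin at baseline". The cholestasis wording ends the first criterion (normal baseline ALT, AST and bilirubin). The second criterion (any of the three elevated at baseline) follows with its own thresholds and no mention of cholestasis.

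**Section 6.5.1.2, text under Table 6-3.** Clinical judgment guides management in general, with an exception that begins "However, for events requiring a discontinuation in", names Tables 6-4 to 6-8, and ends "treatment must be discontinued".

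**Section 6.5.1.2.1.** The same two baseline groups appear in one list. The second is introduced by "For patients with elevated AST or ALT or TBIL value at baseline". The section then says "Medical review needs to ensure that liver test elevations are not caused by cholestasis", which applies to everyone on the list. Without bone metastasis, cholestasis is defined as "ALP elevation > 2.0 x ULN with R value < 2 in patients without bone metastasis". With bone metastasis, it is a raised liver fraction of ALP. The rule that follows is "In the absence of cholestasis, these patients must be immediately discontinued from study drug treatment".

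**The concern.** The two passages cover the same patients, use the same laboratory criterion and concern the same decision, but they attach different conditions to it. In the table, cholestasis matters for normal-baseline patients and is not mentioned for the others. In the section it matters for both groups.

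Elevated-baseline patients are part of the planned population. Inclusion criterion 8a admits AST and ALT below 2.5 x ULN, or below 5 x ULN with liver metastasis. The text is also live: Amendment 4 lists Table 6-5 among its updates, and it lets placebo patients cross over to ribociclib.

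What is at stake is whether two sites with the same patient reach the same stopping decision. That decision feeds the final-report SAP's summaries of reasons for discontinuing ribociclib/placebo (Section 3.5.5) and of adverse events leading to study drug discontinuation (Section 3.7.1.4).

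**Working it through.** The plan states no figure on this point, so the check compares the texts and then traces one constructed patient through both rules.

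**Side by side, for patients who meet the combined criterion**

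| Baseline tests | Cholestasis | Table 6-5 | Section 6.5.1.2.1 |
|---|---|---|---|
| Normal | Absent | Discontinue | Discontinue |
| Normal | Present | Row not triggered | No mandate stated |
| Elevated | Absent | Discontinue | Discontinue |
| Elevated | Present | Discontinue | No mandate stated |

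The first three rows agree. Only the fourth conflicts.

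**Constructed patient.** The values are assumed, the definitions are the protocol's, and all figures are multiples of ULN. The patient has no bone metastasis. Baseline ALT is 1.5 and total bilirubin 0.9. On study, ALT is 4.0, total bilirubin 2.5 and ALP 3.0.

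1. Baseline group: ALT 1.5 is above ULN, so the elevated-baseline criterion applies. The patient is within eligibility on these tests (ALT below 2.5, bilirubin below 1).
2. Transaminase part: 2 x baseline = 2 x 1.5 = 3.0. ALT 4.0 exceeds this and also exceeds 3.0 x ULN. Met.
3. Bilirubin part: 2 x baseline = 2 x 0.9 = 1.8. Bilirubin 2.5 exceeds this and also exceeds 2.0 x ULN. Met.
4. Cholestasis: ALP 3.0 exceeds 2.0 x ULN. R = ALT/ALP = 4.0/3.0 = 1.33, which is below 2. Present.
5. Table 6-5: the criterion is met and has no cholestasis condition, so the entry is to discontinue, and Section 6.5.1.2 makes it binding.
6. Section 6.5.1.2.1: the discontinuation sentence requires absence of cholestasis, so it is not triggered.

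**Is there text that settles it?**

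- The line under the title of Table 6-5 sends the reader to Section 6.5.1.2.1 for more information. It sets no order of precedence.
- The table's footnote on transaminases asks for alternative causes to be excluded, obstruction among them, but only ahead of an interruption or reduction. It does not mention discontinuation.
- Section 7.1.3 refers treatment discontinuation for toxicity back to Section 6.5, which contains both rules.
- A misplaced phrase from PDF extraction is unlikely. Section 7.2.2.5.6 (hepatic marker sampling) separately attaches the cholestasis wording to its normal-baseline bullet only.

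**The case against.** The strongest reply is that this is a wording gap and not a head-on contradiction. It rests on four points.

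1. **The section is silent on cholestatic patients.** It never says that they may continue, so a site that follows the table breaches nothing in the section. This stands. A reader might infer that Section 6.5.1.2.1 permits continuation, or that discontinuation is 100% under one passage and 0% under the other. The text supports only that one passage contains a mandate and the other does not.
2. **Scope.** Section 6.5.1.2 introduces Tables 6-4 to 6-8 as guidance for adverse reactions related to study drug. This stands and narrows the point. A reader might take biliary compression by liver metastases as the typical conflict, but an event attributed to metastases falls outside that scope. What remains is a cholestatic pattern handled as related to study drug.
3. **The cross-reference means that both passages are to be read together.** This stands in part. The reader is directed to the section, but on arrival finds a condition that the table lacks and no statement of which prevails.
4. **Liver-injury reporting is unaffected.** This stands. A reader might infer that the conflict changes which cases count as potential drug-induced liver injury. The end of Section 6.5.1.2.1 sets that serious adverse event definition separately: the section's own laboratory criteria, confirmed on repeat testing, with no alternative cause found. It does not depend on the table's discontinuation row.

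It can also be said that no efficacy endpoint or error rate is touched and that PFS and OS have already been met. That is correct, and it limits the weight of the point to safety conduct and safety reporting.

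**Conclusion.** Wrong as written: this is an internal inconsistency and does not challenge a design choice. It affects patients who have elevated AST, ALT or bilirubin at baseline, reach the combined criterion on study, meet the protocol's cholestasis definition, and have the event handled as related to study drug. For them Table 6-5 contains a binding instruction to discontinue and Section 6.5.1.2.1 contains none. The documents do not give their number. Since all four conditions must hold together, it is probably small.

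The conclusion rests on two readings. First, the cholestasis phrase in the table belongs to the criterion that it closes, which Section 7.2.2.5.6 supports. Second, the patients in the section's discontinuation sentence are both groups listed just above it. No view is taken on which rule is clinically right.

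**What to change.** Reconcile Table 6-5 and Section 6.5.1.2.1 so that both state in the same words, for each baseline group, whether and how cholestasis conditions discontinuation. The sponsor's safety team should decide the form. If cholestasis remains a condition, the section should also state what applies to a patient who has it, because it is silent now. If the table and section are meant to differ, one sentence saying which governs would be enough.

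The cost is a phrase in one passage or the other, carried by the next amendment or a clarification to sites. No analysis needs to change.

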### 6.5.1.2.1 Additional follow-up for hepatic toxicities

Increase in transaminases combined with total bilirubin (TBIL) increase may be indicative of drug-induced liver injury (DILI), and should be considered as clinically important events. The threshold for potential DILI may depend on the patient's baseline AST/ALT and TBIL value; patients meeting any of the following criteria will require further follow-up as outlined below:

- For patients with normal ALT and AST and TBIL value at baseline: AST or ALT > 3.0 x ULN combined with TBIL > 2.0 x ULN
- For patients with elevated AST or ALT or TBIL value at baseline: [AST or ALT > 2 x baseline AND > 3.0 x ULN] OR [AST or ALT > 8.0 x ULN], whichever is lower, combined with [TBIL > 2 x baseline AND > 2.0 x ULN]

Medical review needs to ensure that liver test elevations are not caused by cholestasis, defined as: ALP elevation > 2.0 x ULN with R value < 2 in patients without bone metastasis, or elevation of ALP liver fraction in patients with bone metastasis.

[figure not shown]
Note: The R value is calculated by dividing the ALT by the ALP, using multiples of the ULN for both values. It denotes the relative pattern of ALT and/or ALP elevation is due to cholestatic or hepatocellular liver injury or mixed type injury.

In the absence of cholestasis, these patients must be immediately discontinued from study drug treatment, and repeat LFT testing as soon as possible, preferably within 48 hours from the awareness of the abnormal results. The evaluation should include laboratory tests, detailed history, physical assessment and the possibility of liver metastasis or new liver lesions, obstructions/compressions, etc.

Hepatic toxicity monitoring includes the following LFTs: albumin, ALT, AST, total bilirubin, direct and indirect bilirubin, alkaline phosphatase (fractionated if alkaline phosphatase is grade 2 or higher), creatine kinase, prothrombin time (PT)/INR and GGT. For patients with Gilbert Syndrome: total and direct bilirubin must be monitored, intensified monitoring applies to changes in direct bilirubin only.

Close observation is recommended in case of AST, ALT, and/or bilirubin increase requiring dose interruption, which involves:

- Repeating liver enzyme and serum bilirubin tests **two or three times weekly**. After dose resumption repeat liver enzyme and bilirubin tests twice weekly during the first 2 weeks,

afterwards the frequency of re-testing can decrease to once a week or less if abnormalities stabilize or return to normal values.

[figure not shown]
- Obtaining a more detailed history of current symptoms.
- Obtaining a more detailed history of prior and/or concurrent diseases, including history of any pre-existing liver conditions or risk factors.
- Obtaining a history of concomitant drug use (including non-prescription medications, herbal and dietary supplements), alcohol use, recreational drug use, and special diets.
- Ruling out acute viral hepatitis types A, B, C, D, and E; hepatotropic virus infections (CMV, EBV or HSV); autoimmune or alcoholic hepatitis; NASH; hypoxic/ischemic hepatopathy; and biliary tract disease.
- Obtaining a history of exposure to environmental chemical agents.
- Obtaining additional tests to evaluate liver function, as appropriate (e.g., INR, direct bilirubin).
- Considering gastroenterology or hepatology consultations.
- Assessing cardiovascular dysfunction or impaired liver oxygenation, including hypotension or right heart failure as possible etiologies for liver dysfunction.
- Obtaining a PK sample, as close as possible to last dose of study drug.
- Obtaining a liver biopsy, as clinically indicated, to assess pathological change and degree of potential liver injury.

All cases confirmed on repeat testing, meeting the laboratory criteria defined above, with no other alternative cause for LFT abnormalities identified should be considered as “medically significant”, thus met the definition of SAE (Section 8.2.1), and reported as SAE using the term “potential drug-induced liver injury”. All events should be followed up with the outcome clearly documented. Results of tests as well as other clinically important information will be recorded in the eCRF.

#### 6.5.1.2.2 Additional follow-up for QTcF prolongation

**Table 6-6 Ribociclib/placebo dose adjustment and management recommendation for QTcF prolongation (CTC AE v4.03)**

Grade	Dose Modification
For All Grades	
 
• 1 Check the quality of the ECG and the QT value and repeat if needed.
 
• 2 Perform analysis of serum electrolytes (K+, Ca++, Phos, Mg++). If outside of the normal range, interrupt ribociclib/placebo administration, correct with supplements or appropriate therapy as soon as possible, and repeat electrolytes until documented as normal.
 
• 3 Review concomitant medication usage for the potential to inhibit CYP3A4 and/or to prolong the QT interval.
 
• 4 Check compliance with correct dose and administration of ribociclib/placebo.
 

1* QTcF 450-480 ms	Perform steps 1-4 as directed in “For All Grades.” No dose adjustment required.

2* QTcF 481-500 ms
	
Interrupt ribociclib/placebo. Perform steps 1-4 as directed in “For All Grades.” Perform a repeat ECG within one hour of the first QTcF of <math>\geq 481</math> ms. Repeat ECG as clinically indicated until the QTcF returns to <math><481</math> ms. Restart ribociclib/placebo with dose reduced by 1 dose level. Refer to Table 6-3 for dosing schedule.. If QTcF <math>\geq 481</math> ms recurs, ribociclib should be reduced again by 1 dose level.  Repeat ECGs 7 days and 14 days after dose resumption (then as clinically indicated) for any patients who had therapy interrupted due to QTcF <math>\geq 481</math> ms.


3 QTcF <math>\geq 501</math> ms on at least two separate ECGs
	
Interrupt ribociclib/placebo. Perform steps 1-4 as directed in “For All Grades.” Perform a repeat ECG within one hour of the first QTcF of <math>\geq 501</math> ms. If QTcF remains <math>\geq 501</math> ms, consult with a cardiologist (or qualified specialist) and repeat cardiac monitoring as indicated until the QTcF returns to <math>< 481</math> ms.  
 
If QTcF returns to <math>< 481</math> ms, ribociclib/placebo will be reduced by 1 dose level. Refer to Table 6-3 for dosing schedule.
 
If QTcF remains <math>\geq 481</math> ms after performing steps 1-4 as directed in “For All Grades” discontinue ribociclib/placebo.
 
 Repeat ECGs 7 days and 14 days after dose resumption (then as clinically indicated) for any patients who had therapy interrupted due to QTcF <math>\geq 501</math> ms. If QTcF of <math>\geq 501</math> ms recurs, discontinue ribociclib/placebo

4* [QT/QTcF <math>\geq 501</math> or <math>> 60</math> ms change from baseline] and [Torsades de pointes or polymorphic ventricular tachycardia, or signs/symptoms of serious arrhythmia]
	
Discontinue ribociclib/placebo. Perform steps 1-4 as directed in “For All Grades.”  
 
Obtain local cardiologist (or qualified specialist) consultation and repeat cardiac monitoring as indicated until the QTcF returns to <math><481</math> ms.
 

*All values refer to the average of triplicate measurements
	

**Table 6-7 Ribociclib/placebo dose adjustment and management recommendation for ILD/pneumonitis (CTCAE v4.03)**

Grade	Dose Adjustment and Management Recommendations
1 (asymptomatic)	No dose adjustment required. Initiate appropriate medical therapy and monitor as clinically indicated.
2 (symptomatic)	Interrupt ribociclib dose until recovery to Grade $\leq 1$ , then resume ribociclib at the next lower dose level*.
3 and 4 (severe)	Discontinue ribociclib

\*An individualized benefit-risk assessment should be performed before resuming ribociclib

### 6.5.1.2.3 Guidance for all other adverse reactions

Consider performing an analysis of serum potassium, calcium, phosphorus, and magnesium for all adverse reactions, if indicated. If electrolyte values are outside of the normal range, , interrupt ribociclib/placebo administration, correct electrolytes with supplements or appropriate

therapy as soon as possible, and repeat electrolyte testing until documented normalization of the electrolytes.

Patients who experience non-acute renal impairment of grade 2 or higher during the treatment period should discontinue ribociclib/ placebo treatment and should be followed for safety assessments. For all other adverse events, including Toxic Epidermal Necrolysis (TEN), which is a grade 4 event by CTCAE, please follow recommendations in [Table 6-8](#).

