**Table 1-2 Adverse events suspected to be study drug related in [\[CLEE011X2108\]](#)**

Table below is update with data including a cutoff incidence of more than 15%

Preferred term	All grades n (%)	Grade 3/4 n (%)
-Total	13 (100)	11 (84.6)
NEUTROPENIA	9 (69.2)	8 (61.5)
FATIGUE	9 (69.2)	2 (15.4)
NAUSEA	6 (46.2)	0

---

ANAEMIA	6 (46.2)	0
DECREASED APPETITE	5 (38.5)	0
WHITE BLOOD CELL COUNT	4 (30.8)	2 (15.4)
DIARRHOEA	4 (30.8)	0
VOMITING	3 (23.1)	0
THROMBOCYTOPENIA	3 (23.1)	0
ALANINE AMINOTRANSFERASE	2 (15.4)	1 (7.7)
ASPARTATE AMINOTRANSFERASE	2 (15.4)	1 (7.7)
PRURITUS	2 (15.4)	0
PLATELET COUNT DECREASED	3 (23.1)	0
DYSGEUSIA	2 (15.4)	0
ELECTROCARDIOGRAM QT	2 (15.4)	0
NEUTROPHIL COUNT DECREASED	2 (15.4)	2 (15.4)
BLOOD CREATININE INCREASED	2 (15.4)	0
LYMPHOCYTE COUNT DECREASED	2 (15.4)	0
ORAL PAIN	2 (15.4)	0

---

Preliminary results of ribociclib in combination with fulvestrant suggest that this combination is safe and tolerable. Preliminary PK analysis suggests that ribociclib (600 mg) and fulvestrant (500 mg) exposures were not affected in combination treatment. The best response for all 7 (100%) patients has been stable disease thus far.

Refer to the LEE011 (ribociclib) [Investigators Brochure] for more details.

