**For assessment of patients’ eligibility to the study, only laboratory results from the central laboratory will be used.**

**Table 6-4 Ribociclib/Placebo dose adjustment and management recommendations for hematological adverse reactions (CTC AE v4.03)**

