**The results of the local laboratory will be recorded in the eCRF if any of the following criteria are met:**

Toxicity/Grade	Dose Adjustment and Management Recommendations
Thrombocytopenia	
Grade 1 (≥75 x 10  /L)	No dose adjustment required.
Grade 2 (≥50 x 10  /L – <75 x 10  /L)	Dose interruption until recovery to grade ≤1. Re-initiate ribociclib/placebo at the same dose.
Grade 3 (≥25 x 10  /L - <50 x 10  /L)	Dose interruption until recovery to grade ≤1. Re-initiate ribociclib/placebo at the same dose level. If toxicity recurs at grade 3: temporary dose interruption until recovery to grade ≤1 and reduce ribociclib/placebo to the next lower dose level.

Toxicity/Grade	Dose Adjustment and Management Recommendations
Grade 4 (<25 x 10  /L)	Dose interruption until recovery to grade ≤1. Re-initiate ribociclib/placebo at the next lower dose level. If toxicity recurs at grade 4: discontinue ribociclib/placebo.
Absolute neutrophil count (ANC)	
Grade 1 (≥1.5 x 10  /L)	No dose adjustment required.
Grade 2 (≥1.0 - <1.5 x 10  /L)	No dose adjustment required.
Grade 3 (≥0.5 - <1.0 x 10  /L)	Dose interruption until recovery to ≥1.0 x 10  /L. Re-initiate ribociclib/placebo at the same dose level. If toxicity recurs at grade 3: temporary dose interruption until recovery to ≥ 1.0 x 10  /L. If resolved in ≤7 days, then maintain dose level. If resolved in >7 days, then reduce ribociclib/placebo dose to the next lower dose level.
Grade 4 (<0.5 x 10  /L)	Dose interruption until recovery to ≥ 1.0 x 10  /L. Re-initiate ribociclib/placebo at the next lower dose level. If toxicity recurs at grade 4: temporary dose interruption until recovery to ≥1.0 x 10  /L and reduce ribociclib/placebo at the next lower dose level.
Febrile neutropenia	
Grade 3 ANC <1.0 x 10  /L with a single temperature of >38.3 °C (101 °F) or a sustained temperature of ≥38 °C (100.4 °F) for more than one hour	Dose interruption until improvement of ANC ≥ 1.0 x 10  /L and no fever. Restart at the next lower dose level. If febrile neutropenia recurs, discontinue ribociclib/placebo.
Grade 4 Life-threatening consequences; urgent intervention indicated	Discontinue ribociclib/placebo.
Anemia (Hemoglobin)	
Grade 1 (≥10.0 – LLN g/dL)	No dose adjustment required.

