**Table 6-8 Ribociclib/placebo dose adjustment and management recommendation for all other adverse reactions**

Grade	Dose Adjustment and Management Recommendations
1	No dose adjustment recommended. Initiate appropriate medical therapy and monitor.
2	Dose interruption until recovery to grade $\leq 1$ . Initiate appropriate medical therapy and monitor. Re-initiate ribociclib/placebo at the same dose. If the same toxicity recurs at grade 2, interrupt ribociclib/placebo until recovery to grade $\leq 1$ . Re-initiate ribociclib/placebo at the next lower dose level.
3	Dose interruption until recovery to grade $\leq 1$ . Initiate appropriate medical therapy and monitor. Re-initiate ribociclib/placebo at the next lower dose level. If toxicity recurs at grade 2: temporary dose interruption until recovery to grade $\leq 1$ and reduce ribociclib/placebo dose the next lower dose level. If toxicity recurs at grade 3, discontinue ribociclib/placebo.
4	Discontinue ribociclib/placebo and treat with appropriate medical therapy.

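### White cell decrease has no row in the haematology dose table (Table 6-4), so the plain text sends it to Table 6-8, which can contradict the neutrophil row for the same blood count

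*Protocol*

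**What the plan says.** Protocol section 6.5.1.2 offers Tables 6-4 to 6-8 as recommendations for managing reactions related to study drug. The text under Table 6-3 leaves management to the physician's judgment, except that where one of these tables calls for discontinuation, treatment must stop.

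Table 6-4 is titled for "dose adjustment and management recommendations for hematological adverse reactions (CTC AE v4.03"). It covers thrombocytopenia, ANC, febrile neutropenia and anaemia, with no row for white cells or lymphocytes. In the ANC rows, grades 1 and 2 read "No dose adjustment required". Grade 3 is held until ANC reaches 1.0 × 10⁹/L, then: "Re-initiate ribociclib/placebo at the same dose level. If toxicity recurs at grade 3: temporary dose interruption until recovery". On recurrence, "If resolved in ≤7 days, then maintain dose level"; slower recovery means the next lower level. Grade 4 means a hold and a lower level, both at first occurrence and on recurrence.

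Section 6.5.1.2.3 covers the remainder: "For all other adverse events, including Toxic Epidermal Necrolysis (TEN), which is a grade 4 event by CTCAE, please follow recommendations in" Table 6-8. There, grade 2 is held until grade 1 or better, then restarted at the same dose, or one level lower if it recurs. The grade 3 row includes "Re-initiate ribociclib/placebo at the next lower dose level. If toxicity recurs at grade 2: temporary dose interruption until recovery to grade" 1 or better, and ends in discontinuation if grade 3 recurs. The grade 4 row is "Discontinue ribociclib/placebo and treat with appropriate medical therapy".

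**The concern.** WBC and its differential come from one haematology test (Protocol Table 7-4), and neutrophils are part of WBC. A fall in neutrophils therefore lowers WBC in the same sample. If the site manages the event as neutropenia, Table 6-4 applies. If it also records leukopenia or a WBC decrease as a drug-related reaction, the wording of 6.5.1.2.3 brings in Table 6-8. Whether the patient continues, steps down or stops can then turn on the recorded term.

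These are expected events. In the combination data of Protocol Table 1-2 (n = 13), neutropenia was reported in 69.2% (grade 3/4 61.5%) and "WHITE BLOOD CELL COUNT" in 30.8% (grade 3/4 15.4%). In the single-agent data of section 1.2.1.2.1, leukopenia was 22% and WBC decrease 22.7%. The primary-analysis SAP (section 3.9.1.5) lists leukopenia and neutropenia as separate groupings of special interest. An unclear dose rule would feed into the planned summaries of dose reductions, interruptions and discontinuations and into the adverse events leading to them, besides its bearing on patients still receiving ribociclib, including those who cross over under Amendment 4.

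**Working it through.** The plan states no figure for this point, so there is none to reproduce.

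**Step 1: grade cut-offs (SAP Appendix 1, × 10⁹/L).** ANC: grade 2 is 1.0 to <1.5, grade 3 is 0.5 to <1.0, grade 4 is <0.5. WBC: grade 2 is 2.0 to <3.0, grade 3 is 1.0 to <2.0, grade 4 is <1.0. Recovery of WBC to grade 1 or better therefore means 3.0 or more.

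**Step 2: the two tables at equal grade.**

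| Event | Table 6-4, ANC row | Table 6-8, if applied to WBC |
|---|---|---|
| Grade 2, first | No adjustment | Hold to WBC ≥3.0, same dose |
| Grade 3, first | Hold to ANC ≥1.0, same dose | Hold to WBC ≥3.0, next lower level |
| Grade 3, recurrent | Hold; lower level only if recovery takes >7 days | Discontinue |
| Grade 4 | Hold to ANC ≥1.0, next lower level | Discontinue |

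**Step 3: can one sample trigger both?** WBC = ANC + lymphocytes + other cells. The counts below are illustrative.

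- 1.2 + 1.2 + 0.3 = 2.7: ANC grade 2, WBC grade 2. No adjustment against a hold.
- 0.8 + 0.8 + 0.3 = 1.9: ANC grade 3, WBC grade 3. Same dose against the next lower level.
- 0.8 + 1.2 + 0.3 = 2.3: ANC grade 3, WBC grade 2. At a first event both tables hold and restart at the same dose; the recovery threshold and recurrence rule differ.
- 0.4 + 1.0 + 0.2 = 1.6: ANC grade 4, WBC grade 3. At a first event both hold and restart one level lower; again the threshold and recurrence rule differ.
- 0.4 + 0.4 + 0.1 = 0.9: ANC grade 4, WBC grade 4. Reduce against discontinue.

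**Step 4: how often, under assumed distributions.** The documents give no joint distribution of cell counts. Assumptions: ANC uniform within its grade band (0 to 0.5 for grade 4); lymphocytes lognormal with log-SD 0.35; other cells lognormal with median 0.3 and log-SD 0.4; all independent. The lymphocyte median varies across columns. Entries are simulated percentages of samples.

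| Lymphocyte median | 0.8 | 1.0 | 1.2 | 1.5 |
|---|---|---|---|---|
| ANC grade 2: WBC grade 2 or worse | 93 | 82 | 67 | 44 |
| ANC grade 3: WBC below 3.0 | 99 | 96 | 90 | 75 |
| ANC grade 3: WBC grade 3 | 62–63 | 41 | 25 | 11 |
| ANC grade 4: WBC grade 3 | 83 | 78 | 65 | 44 |
| ANC grade 4: WBC grade 4 | 10 | 4 | 1.5 | 0.4 |

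For grade 3 ANC, subtracting row 3 from row 2 leaves about 37, 55, 65 and 64% with WBC grade 2, where the first-event dose is the same in both tables.

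**Step 5: lymphocytes.** Take ANC 2.5, lymphocytes 0.4, other 0.3, so WBC 3.2. The ANC row asks for nothing, while Table 6-8 would treat the lymphocyte value as grade 3. Lymphocytes are not counted in ANC, so the ANC row does not address them. This is a missing row.

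**The case against.** **Table 6-4 may be meant to cover the whole haematology class.** Its title is general, and section 7.1 points to it for haematologic toxicity, so the catch-all could be read as excluding that class. But section 7.1 cites the table only for monitoring frequency. On this reading WBC decrease has no dose rule at all, so the text still needs repair.

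**A low WBC explained by neutropenia need not be a second event.** Section 8.1.2.1 says a result that corresponds to an already reported event need not be recorded separately, and section 8.1.1 prefers a diagnosis to individual signs. This is fair, and it limits the conflict to sites that do record the WBC decrease as a reaction. Arguing that the hold itself makes the value an adverse event would be circular, because Table 6-8 asks for the hold only once there is a reaction. Still, the recording rule does not say which table governs, and Table 1-2 shows WBC decrease being recorded as an event in the same study as neutropenia.

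**Clinical judgment covers most of it.** This stands for the grade 2 and first grade 3 differences. It does not reach grade 4 or recurrent grade 3 under Table 6-8, where discontinuation is mandatory.

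**Equal-grade pairing overstates the clash.** This also stands: WBC grade often sits one below ANC grade. A reader might infer that 75–99% of grade 3 ANC samples receive opposing dose instructions. They do not, since that share includes the WBC grade 2 samples, which restart at the same dose at a first event.

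**Conclusion.** The point holds for white cell decrease. Followed as written, Tables 6-4 and 6-8 can give contradictory instructions for one blood count, and two of the four differences involve a mandatory discontinuation. That reading of the text needs no distributional assumption. It does require that the WBC decrease be recorded as a drug-related reaction and that the catch-all be read plainly.

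The frequencies rest wholly on the assumed distributions in Step 4 and describe laboratory samples, not recorded events. The differences at grade 2 and first grade 3 carry most of the practical weight. The starkest clash, at grade 4, would be uncommon (about 0.4–10% of grade 4 ANC samples).

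Three stronger readings are not supported. Lymphopenia does not contradict the neutrophil row; it simply lacks a rule of its own. Nothing in the documents shows that any patient was reduced or stopped because of this, and they give no placebo-arm leukopenia figure from which to size a difference between arms. Nor does the point reopen the efficacy conclusions: PFS and OS have been met and section 10.7.2 makes later analyses descriptive. What remains is the dosing of patients still on ribociclib or crossing over to it, and the interpretation of the dose-modification summaries.

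**What to change.** Reconcile Table 6-4, section 6.5.1.2.3 and Table 6-8. Add one row or sentence to section 6.5.1.2 stating which table governs a white cell decrease, and which governs a lymphocyte decrease, each with and without concurrent neutropenia, so that one blood count yields one instruction. Which instruction applies is a clinical decision for the sponsor's safety team; no view is taken here. The cost is a short protocol amendment or clarification letter to sites, with no extra data collection.
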